### 5.6.3 Supportive Care Guidelines

Imprime PGG supportive care guidelines should follow the ASCO Clinical Practice Guidelines.

Subjects should receive appropriate supportive care measures as deemed necessary by the treating Investigator. Suggested supportive care measures for the management of adverse events with potential immunologic etiology are outlined below, along with the dose modification guidelines presented earlier in Section 5.2.1.2.2 in Table 1. Where appropriate, these guidelines include the use of oral or intravenous treatment with corticosteroids as well as additional anti-inflammatory agents if symptoms do not improve with administration of corticosteroids. Note that several courses of steroid tapering may be necessary as symptoms may worsen when the steroid dose is decreased. For each disorder, attempts should be made to rule out other causes such as metastatic disease or bacterial or viral infection, which might require additional supportive care. The treatment guidelines are intended to be applied when the Investigator determines the events to be related to pembrolizumab.

Note: If after the evaluation the event is determined not to be related to pembrolizumab, the Investigator does not need to follow the treatment guidance. Refer to [Section 5.2.1.2.2](#) for guidelines regarding dose modification and supportive care.

It may be necessary to perform conditional procedures such as bronchoscopy, endoscopy, or skin photography as part of evaluation of the event.

See [Section 5.2.1.2.2](#) for treatment guidelines for subjects who experience an infusion reaction associated with administration of pembrolizumab.

## **5.7 Diet/Activity/Other Considerations**

### **5.7.1 Diet**

Subjects should maintain a normal diet unless modifications are required to manage an adverse event such as diarrhea, nausea or vomiting.

### **5.7.2 Contraception**

It is unknown what the effects of Imprime PGG may be during a pregnancy.

Pembrolizumab may have adverse effects on a fetus in utero. Furthermore, it is not known if pembrolizumab has transient adverse effects on the composition of sperm.

For this trial, male subjects will be considered to be of non-reproductive potential if they have azoospermia (whether due to having had a vasectomy or due to an underlying medical condition).

Female subjects will be considered of non-reproductive potential if they:

- (1) Are postmenopausal (defined as at least 12 months with no menses without an alternative medical cause; in women < 45 years of age a high follicle stimulating hormone (FSH) level in the postmenopausal range may be used to confirm a postmenopausal state in women not using hormonal contraception or hormonal replacement therapy. In the absence of 12 months of amenorrhea, a single FSH measurement is insufficient.)

OR

- (2) Have had a hysterectomy and/or bilateral oophorectomy, bilateral salpingectomy or bilateral tubal ligation/occlusion, at least 6 weeks prior to screening

OR

- (3) Have a congenital or acquired condition that prevents childbearing.

Female and male subjects of reproductive potential must agree to avoid becoming pregnant or impregnating a partner, respectively, while receiving study drug and for 120 days after the last dose of study drug by complying with one of the following:

- (1) Practice abstinence† from heterosexual activity;

OR

- (2) Use (or have their partner use) acceptable contraception during heterosexual activity.

Acceptable methods of contraception are the following†:

- Single method (1 of the following is acceptable):
  - Intrauterine device (IUD)
  - Vasectomy of a female subject's male partner
  - Contraceptive rod implanted into the skin
- Combination method (requires use of 2 of the following):
  - Diaphragm with spermicide (cannot be used in conjunction with cervical cap/spermicide)
  - Cervical cap with spermicide (nulliparous women only)
  - Contraceptive sponge (nulliparous women only)
  - Male condom or female condom (cannot be used together)
  - Hormonal contraceptive: oral contraceptive pill (estrogen/progestin pill or progestin-only pill), contraceptive skin patch, vaginal contraceptive ring, or subcutaneous contraceptive injection

†Abstinence (relative to heterosexual activity) can be used as the sole method of contraception if it is consistently employed as the subject's preferred and usual lifestyle and if considered acceptable by local regulatory agencies and ERCs/IRBs. Periodic abstinence (eg, calendar, ovulation, sympto-thermal, post-ovulation methods, etc.) and withdrawal are not acceptable methods of contraception.

†If a contraceptive method listed above is restricted by local regulations/guidelines, then it does not qualify as an acceptable method of contraception for subjects participating at sites in this country/region.

Subjects should be informed that taking the study medication may involve unknown risks to the fetus (unborn baby) if pregnancy were to occur during the study. In order to participate in the study, subjects of childbearing potential must adhere to the contraception requirement (described above) from the day of study medication initiation (or 14 days prior to the initiation of study medication for oral contraception) throughout the study period up to 120 days after the last dose of trial therapy. If there is any question that a subject of childbearing potential will not reliably comply with the requirements for contraception, that subject should not be entered into the study.

### 5.7.3 Use in Pregnancy

If a subject inadvertently becomes pregnant while on treatment with either Imprime PGG or pembrolizumab, the subject will immediately be removed from the study. The site will contact the subject at least monthly and document the subject's status until the pregnancy has been completed or terminated.

The outcome of the pregnancy will be reported to the Sponsor without delay and within 24

hours if the outcome is a serious adverse experience (eg, death, abortion, congenital anomaly, or other disabling or life-threatening complication to the mother or newborn). The study Investigator will make every effort to obtain permission to follow the outcome of the pregnancy and report the condition of the fetus or newborn to the Sponsor.

#### **5.7.4 Use in Nursing Women**

It is not known whether either Imprime PGG or pembrolizumab is excreted in human milk. Since many drugs are excreted in human milk, and because of the potential for serious adverse reactions in the nursing infant, subjects who are breast-feeding are not eligible for enrollment into the study.

### **5.8 Subject Withdrawal/Discontinuation Criteria**

#### **5.8.1 Withdrawal/Discontinuation Criteria**

Subjects will be encouraged to complete the study; however, they may voluntarily withdraw at any time without prejudice to future care. The Investigator will provide a written report describing the reason for discontinuation. If a subject discontinues study drug, every effort should be made to complete the assessments scheduled to occur during the Post-Treatment Visit and survival follow-up period. The subject will continue to be followed until completion of the study.

A subject may discontinue study drug for the following medical or administrative reasons:

- Adverse event: If a subject suffers an AE that in the judgment of the Investigator, presents an unacceptable consequence or risk to the subject, the subject may be discontinued from study drug
- Progressive Disease per irRECIST (see [Section 7.3.2](#))
- Subject decision: A subject may voluntarily discontinue from study drug at any time
- Intercurrent illness: A subject may discontinue study drug if, in the judgment of the Investigator, the subject develops an intercurrent illness or complication that is not consistent with the protocol requirements or that, in any way, justifies withdrawal from the study drugs, or that requires treatment with a restricted medication.
- Ineligibility to protocol entry criteria determined
- Lost to follow-up
- Administrative discontinuation: After consultation between the Investigator, the medical monitor, or the Sponsor when appropriate, a subject may be discontinued from study drug for the following administrative reasons:
  - Noncompliance (all occurrences of noncompliance must be documented on the appropriate eCRFs)

- Failure to receive study drug per protocol as defined in [Section 5.2 Trial Treatments](#)
- Failure to comply with protocol requirements
- Refusal of study drug administration (with reason documented)

In all cases, when subjects discontinue study drug, reasonable efforts should be made to monitor the subject for AEs and to complete follow-up assessments following such discontinuation. These efforts should be documented on the appropriate eCRF. The subject will continue to be followed for survival for the duration of the study.

If a subject withdraws consent for follow-up of survival, this must be documented, and no further efforts at contact will be attempted.

### **5.8.2 Discontinuation of Study Therapy After Complete Response**

Discontinuation of treatment may be considered for subjects who have attained a confirmed CR, who have been treated for at least 24 weeks, and who had at least 2 treatments with study medications beyond the date when the initial CR was declared. Subjects who then experience radiographic disease progression may be eligible for up to 1 year of additional treatment with Imprime PGG + pembrolizumab at the discretion of the Investigator if:

- No cancer treatment was administered since the last dose of pembrolizumab
- The subject meets the safety parameters listed in the Inclusion/Exclusion criteria
- The trial is open

Subjects will resume therapy at the same dose and schedule at the time of initial discontinuation. Response or progression in this resumed course of therapy will not count towards the ORR of the primary endpoint in this trial.

### **5.9 Subject Replacement Strategy**

Subjects who discontinue the study treatment due to reasons other than progressive disease or treatment-related adverse events before the first post-baseline scan may be replaced.

### **5.10 Clinical Criteria for Early Trial Termination**

If the Sponsor, Investigator, medical or safety monitor, or appropriate regulatory officials discover conditions arising during the study that indicate the study should be halted or the study site should be terminated, this action may be taken after appropriate consultation among the Sponsor, Investigator, regulatory, and medical and safety monitors.

Conditions that may warrant early termination of the study include, but are not limited to, the following:

- The discovery of an unexpected, serious, or unacceptable risk to enrolled subjects

- A decision on the part of the Sponsor to suspend or discontinue testing, evaluation, or development of the product

Other conditions that may also warrant termination of an individual study site include, but are not limited to, the following:

- Failure of the Investigator to enroll subjects into the study at an acceptable rate
- Failure of the Investigator to comply with pertinent regulations of appropriate regulatory authorities
- Submission of knowingly false information from the research facility to the Sponsor, clinical research associate (CRA), medical and/or safety monitor(s), or appropriate regulatory authority
- Insufficient adherence to protocol requirements

Study termination and follow-up will be performed in compliance with the conditions set forth in the guideline provided by ICH for Technical Requirements for Registration of Pharmaceuticals for Human Use, Good Clinical Practice (ICH GCP): Consolidated Guideline (E6), Sections 4.12, 4.13, 5.20, and 5.21.

## 6.0 TRIAL FLOW CHART

### 6.1 Schedule of Assessments - Study Flow Chart

Cycle		C1	C2	C3	C4	C5	C6	C7 and QOC	C8 and Q4C (C12, C16, C20, C24, C28, C32)	C10 and Q4C (C14, C18, C22, C26, C30, C34)	End of Treatment (EOT)		Post-Treatment (up to 3 Years after Last Subject's 1 st Dose)	
Visit Week	Screening (-30 to -1 Days)*	W1	W4	W7	W10	W13	W16	W19 and Q6W	W22 and Q12W (W34, W46, W58, W70, W82, W94)	W28 and Q12W (W40, W52, W64, W76, W88, W100)		30-Day SFU		
Administrative Procedures														
Informed Consent	X													
Review of Entry Criteria	X													
Urine Pregnancy	X											X		
Medical Hx and Demography	X													
Enrollment	X													
Clinical Procedures / Assessments														
ECOG Status	X	X	X	X	X	X	X	X		X	X	X		
Physical Exam	X											X		
Vital Signs	X													
Weight	X	X	X	X	X	X	X	X		X	X			
AE Monitoring (Every Visit in Cycle)	X	X	X	X	X	X	X	X		X	X	X		
Administration of Pembrolizumab (D1 of Each Cycle)		X	X	X	X	X	X	X		X				
Administration of Imprime PGG (D1, D8, D15 of Each Cycle)		X	X	X	X	X	X	X		X				
Concomitant Medications (Every Visit in Cycle)		X	X	X	X	X	X	X		X	X	X		
Laboratory Procedures / Assessments														
Hematology**	X*	X	X	X	X	X	X	X		X	X	X		

10 August 2017

Confidential – Biothera Pharmaceuticals, Inc.

Cycle		C1	C2	C3	C4	C5	C6	C7 and QOC	C8 and Q4C (C12, C16, C20, C24, C28, C32)	C10 and Q4C (C14, C18, C22, C26, C30, C34)	End of Treatment (EOT)		Post-Treatment (up to 3 Years after Last Subject's 1 st Dose)	
Visit Week	Screening (-30 to -1 Days)*	W1	W4	W7	W10	W13	W16	W19 and Q6W	W22 and Q12W (W34, W46, W58, W70, W82, W94)	W28 and Q12W (W40, W52, W64, W76, W88, W100)		30-Day SFU		
CBC/Differential (Pre-Imprime infusion and 4 Hr Post-SOI of Imprime: Q4C after C2, EOT)*		X	X				X			X	X			
PBMC (Pre-Imprime infusion and EOI of Imprime: C1, C2, C6, EOT)		X	X				X				X			
RNA/DNA (Pre-Imprime infusion and EOI of Pembro: Q4C after C2, EOT)		X	X				X			X	X			
Serum Chemistry° (QOC, EOT, SFU)	X*	X		X		X		X			X	X		
Coagulation Tests	X*													
Serum ABA (Pre-Imprime Infusion and EOI of Imprime: Q4C after C6, EOT)	X (within 90 days)	X	X	X	X	X	X			X	X			
Serum Cytokines & Complement (Pre-Imprime Infusion and EOI of Imprime: Q4C after C6, EOT)		X	X	X	X	X	X			X	X			
PK (C1, C3 only)		X		X										
Urinalysis	X													
12-Lead ECG	X													
Efficacy Measurements														
CT Scan with Contrast or MRI (Q6W/QOC)	X		X (C2 end)		X (C4 end)		X (C6 end)		X (Cycle end)	X (Cycle end)				

Cycle		C1	C2	C3	C4	C5	C6	C7 and QOC	C8 and Q4C (C12, C16, C20, C24, C28, C32)	C10 and Q4C (C14, C18, C22, C26, C30, C34)	End of Treatment (EOT)		Post-Treatment (up to 3 Years after Last Subject's 1 st Dose)	
Visit Week	Screening (-30 to -1 Days)*	W1	W4	W7	W10	W13	W16	W19 and Q6W	W22 and Q12W (W34, W46, W58, W70, W82, W94)	W28 and Q12W (W40, W52, W64, W76, W88, W100)		30-Day SFU		
Tumor Biopsies														
Archival Biopsy (if feasible) (Sample 1)	X													
Biopsy before First Dose of Treatment (if feasible) (Sample 2)		X												
Biopsy after C2 Complete but before C3 Dosing (if feasible) (Sample 3)				X										
Biopsy at Time of Response or Progression, or EOT (if feasible) (Sample 4)											X			
Long-Term Follow-up														
Survival Monitoring (Up to 3 Years After Last Subject's 1 st Dose)														X

\*Screening window is 15 days before start of dosing for the following Inclusion Criteria: Organ, Renal, Hematologic, and Coagulation Functions

o Serum Chemistry includes Thyroid Function Panel

\*\*Hematology results may be used without the need for an additional blood draw if Hematology is drawn within approximately 1 hour before start of Imprime PGG infusion

Monthly pregnancy testing should be conducted as per local regulations where applicable.

Note: C = Cycle

W = Week

D8 = Day 8

D15 = Day 15

EOI = End of Infusion of Imprime PGG (unless pembrolizumab has been specified) (Samples collected EOI should be within approximately 30 minutes after infusion ends)

EOT = End of Treatment

Pre-infusion = Before start of Imprime PGG infusion (Samples collected Pre-infusion should be within approximately 1 hour before start of infusion)

SOI = Start of Infusion of Imprime PGG

QOC = Every Other Cycle

Q4C = Every 4th Cycle

Q6W = Every 6 weeks

Q12W = Every 12 weeks

Cycle Assessments:

- C1, C2, C3, C4, C5, C6, EOT, 30-Day SFU, and Post-Treatment are as indicated in the table above
- C7, C9, C11, C13, C15, C17, C19, C21, C23, C25, C27, C29, C31, C33, and C35 have identical assessments
- C8, C12, C16, C20, C24, C28, and C32 have identical assessments
- C10, C14, C18, C22, C26, C30, and C34 have identical assessments

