### 2.1 Trial Design

The study will incorporate Simon's optimal 2-stage design with sample size fixed at 12 subjects each in Stage 1 for advanced melanoma and for Triple Negative Breast Cancer (TNBC) subjects. The safety criterion of  $\leq 4$  (or  $\leq 33\%$ ) subjects with Grade 3/4 adverse events in Cycle 1 within either tumor type must be met in order to proceed to Stage 2. The starting dose is 4 mg/kg for Imprime PGG. In the event there are a total of  $> 4$  (or  $> 33\%$ ) of subjects with Grade 3/4 adverse events in Cycle 1, the dose of Imprime PGG will be reduced to 2 mg/kg, and Stage 1 will be repeated at a dose of 2 mg/kg with an additional cohort of n=12 subjects. For the dose that meets the safety criterion in Stage 1, at least 1 response in melanoma subjects and 1 response in TNBC subjects amongst the 12 subjects within each tumor type must be observed in order to proceed to Stage 2.

Stage 2 will enroll an additional 17 subjects with melanoma, and 29 subjects with TNBC. For the dose that meets the Stage 1 safety criterion, success will be declared if at least 4 amongst the total of up to 29 subjects with melanoma, and 5 amongst the total of up to 41 subjects with TNBC achieve an objective response.

The study population will be those having failed front-line therapy, defined as any treatment regimen or regimens used specifically in the treatment of metastatic disease. Refer to [Section 5.1 on Entry Criteria](#) for the study-specific requirements.

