### 7.1 Visit Windows

All treatment visits should occur on the visit days specified in [Table 6.1, Schedule of Assessments](#). However the following visit windows, while not desirable, are acceptable:

- For study medication administration, a visit window of +/- 3 days
- For hematology and chemistry laboratories, a visit window of - 3 days
- For imaging, a visit window of +/- 7 days (which should follow calendar days and not be adjusted for cycle delays)
- For the End of Study Visit, a visit window of +3 days
- For the 30-Day SFU Visit, a visit window of -7 days
- For Every-2-Month Survival Monitoring, a visit window of +/- 7 days

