### 7.3 Treatment Period (Treatment Cycles)

Study Day 1 is defined as the day of the first dose of study medication.

The study treatment period will be divided into treatment cycles. Each cycle will be 3 weeks in duration and defined by the frequency of pembrolizumab administration. During each cycle, subjects will dose weekly with Imprime PGG for all 3 weeks (Days 1, 8, and 15). Pembrolizumab will be dosed on D1 of each 3-week cycle. Subjects will be dosed until

disease progression or death or study termination or 2 years or until any of the criteria for study drug discontinuation are met (whichever occurs first).

See [Section 5.2.2 Timing of Dose Administration](#) for the order in which the study medications must be administered.

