## **8.0 ADVERSE EVENTS (SERIOUS AND NON-SERIOUS)**

### **8.1 Non-serious Adverse Events**

#### **8.1.1 Definition of Adverse Event and Non-serious Adverse Event**

The following definition of adverse event will be used for the study:

Any untoward medical occurrence in a study subject administered a pharmaceutical product and which does not necessarily have to have a causal relationship with this treatment. An adverse event can therefore be any unfavorable and unintended sign (including an abnormal laboratory finding), symptom, or disease temporally associated with the use of a medicinal (investigational) product, whether or not related to medicinal (investigational) product.

This definition includes any abnormalities or anomalies that were not seen at baseline or which worsened during the course of the study, if present at baseline. Disease progression, and events caused by disease progression, will be considered an efficacy endpoint and should not be reported as an AE, even if the event results in hospitalization. Therefore progression of the cancer under study is not considered an adverse event.

A “non-serious” AE is any event that does not meet the definition of “serious adverse event” (SAE) as presented in [Section 8.2](#) below.

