12.2 Adverse Events

All subjects will be assessed regularly for the potential occurrence of adverse events (AEs) from the date of informed consent to 30 days after the last dose of study drug. The incidence of treatment-emergent AEs (TEAEs) will be summarized and tabulated using MedDRA (version 18.1), by System Organ Class (SOC) and Preferred Term (PT). A TEAE is defined as an AE that first occurs or worsens in severity on or after the first dose of any study drug and within 30 days after the last dose of any study drug.

The National Cancer Institute Common Terminology Criteria for Adverse Events (CTCAE) (Version 4.03) will be used to grade both clinical and laboratory AEs. A subject with several occurrences of the same AE will be counted once and classified by the most severe occurrence. AEs with missing severity ratings will be classified as having unknown severity.

An overview summary of AEs will be produced, which will include counts and percentages of subjects with any AEs and Grade III/IV AEs, AEs and Grade III/IV AEs related to study treatment, SAEs, SAEs related to study treatment, fatal SAEs, infusion reactions, AEs leading to dose delayed, dose reduced, and dose withdrawn for Imprime PGG, AEs leading to dose delayed and dose withdrawn for pembrolizumab, and AEs leading to study treatment discontinuation. AEs related to study treatment will be further categorized as AEs related to Imprime PGG and/or pembrolizumab, Imprime PGG only, pembrolizumab only, and both Imprime PGG and pembrolizumab.

A treatment-related AE is defined as an AE for which the investigator classifies the relationship to study treatment as “Yes”. A worst-case scenario approach will be taken to handle missing data, i.e. AEs related to study treatment will include events with the relationship to study treatment as ‘YES’ or missing. Adverse event data will be reviewed periodically to identify infusion reactions, new cancers, and events related to pembrolizumab overdose ($\geq 1000\text{mg}$).

The AE summary tables will use the following algorithms for counting subjects:

- **Preferred term rows:** each subject is counted once within each unique preferred term at the maximum grade. For example, if a subject has two headaches, the subject is counted only once under the preferred term “Headache”. Subjects experiencing the same AE preferred term several times with different grades will only be counted once with the maximum grade.

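### The Stage 1 criterion counts Grade 3/4 events in Cycle 1, but continuing subjects have no scheduled serum chemistry after Day 1 until Cycle 3 Day 1, so the count can only err low

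*Protocol*

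**What the plan says.** **Chemistry schedule.** In Protocol Section 6.1 the row "Serum Chemistry° (QOC, EOT, SFU" is marked at Screening, C1, C3, C5, C7 and every second cycle after that, End of Treatment, and the 30-day safety visit. It is blank at C2. The key gives "QOC = Every Other Cycle", which agrees with the marks. Section 7.3.10 refers back to this chart for laboratory timing and adds no other time point.

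**Window.** Section 7.1 states: "For hematology and chemistry laboratories, a visit window of - 3 days". The window has no forward side.

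**Cycles and dosing.** Section 7.3: "Each cycle will be 3 weeks in duration and defined by the frequency of pembrolizumab administration". The flow chart row "Administration of Pembrolizumab (D1 of Each Cycle" puts the second pembrolizumab dose at C2 Day 1. Imprime PGG is given on Days 1, 8 and 15 of each cycle.

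**Decision rule.** Section 2.1 requires that a limit of 4 of 12 "subjects with Grade 3/4 adverse events in Cycle 1 within either tumor type must be met in order to proceed to Stage 2". Section 9.1.1 and SAP Section 4 carry the same criterion. If it is exceeded at the starting dose, Stage 1 is repeated at the lower Imprime PGG dose.

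**What counts as an event.** The adverse event definition in Section 8.1.1 covers any unfavourable sign, "including an abnormal laboratory finding". SAP Section 12.2 says CTCAE v4.03 "will be used to grade both clinical and laboratory AEs".

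**The concern.** The criterion decides which Imprime PGG dose goes forward and whether Stage 2 opens. Its count is meant to include Grade 3/4 laboratory abnormalities arising in Cycle 1. Several chemistry abnormalities, such as raised transaminases, bilirubin or glucose and electrolyte shifts, can reach Grade 3 without symptoms and are then known only from a blood test. If no test is scheduled between the first dose and the end of Cycle 1, whether such an event enters the count depends on site habit, across about 25 planned sites.

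The error runs one way. A missed event lowers the count, and nothing in the schedule can raise it falsely to compensate. At stake are a criterion that passes somewhat more readily than its wording implies, and Cycle 1 chemistry toxicity rates that look lower than they are.

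**Working it through.** **1. Dates.** With 3-week cycles, week = 1 + 3 × (cycle − 1) and day = 1 + 21 × (cycle − 1).

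| Visit | Week | Nominal day | Chemistry | Hematology | Pembrolizumab |
|---|---|---|---|---|---|
| C1 Day 1 | 1 | 1 | yes | yes | dose 1 |
| C2 Day 1 | 4 | 22 | no | yes | dose 2 |
| C3 Day 1 | 7 | 43 | yes | yes | dose 3 |

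The weeks reproduce the flow chart's own W1, W4 and W7.

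**2. The gap.** With the −3 day window, the C1 sample is taken on Day 1 or up to 3 days before, so it serves as a baseline (the protocol does not state outright that it is pre-dose). The C3 sample falls on Day 40 to 43. The nominal gap is 43 − 1 = 42 days, with a range of 39 to 45. Cycle 1 is Days 1 to 21, so no scheduled chemistry falls in it after Day 1. Before the C3 dosing visit a continuing subject has had 2 pembrolizumab doses (Days 1, 22) and, if none is missed, 6 Imprime PGG doses (Days 1, 8, 15, 22, 29, 36).

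**3. What C3 can and cannot show.** An abnormality still present at Day 40 to 43 will be seen, but cannot be dated to Cycle 1. One that arose and resolved earlier will not be seen.

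**4. Effect on the criterion.** The criterion fails when X > 4, with X binomial on n = 12:

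P(X > 4) = 1 − Σ (x = 0 to 4) C(12, x) p^x (1 − p)^(12 − x)

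Here p is the rate of *detected* events: the true rate minus the share of subjects whose only Grade 3/4 event is an undetected chemistry abnormality. The documents give neither quantity, so both are assumptions.

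| Assumed true rate | Points missed | Detected rate | P(X > 4), full detection | P(X > 4), as detected |
|---|---|---|---|---|
| 20% | 2 | 18% | 0.073 | 0.049 |
| 40% | 2 | 38% | 0.562 | 0.504 |
| 40% | 10 | 30% | 0.562 | 0.276 |

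The loss is 2.4, 5.8 and 28.6 percentage points respectively. The last row is towards the unfavourable end.

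**The case against.** The every-other-cycle schedule is labelled as such and is evidently deliberate. A reader might infer that the criterion is blind to chemistry toxicity. The documents do not support that:

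- A subject who stops treatment in Cycle 1 has End of Treatment chemistry soon after that cycle (Section 7.4.1).
- Adverse events are monitored at every visit, and hematology is drawn at C2.
- Section 7.3.12 allows unscheduled visits and examinations, and Section 8.5 expressly contemplates unscheduled laboratory tests.
- The Stage 2 decision also needs a response, and scans start at Week 6. C3 chemistry may therefore be in hand when the decision is taken, and Section 9.1.6 summarises Grade 3 and higher events at that look without limiting them to Cycle 1.

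These points narrow the concern to silent abnormalities in continuing subjects. They do not remove it. Discretionary testing has no trigger when there are no symptoms, and a C3 value cannot supply a Cycle 1 count.

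A reader might also infer that the second pembrolizumab dose breaches the protocol's own toxicity rules. It does not: Table 1 gives actions once an event is identified and requires no panel before a dose. What can be said is that several of its actions depend on laboratory grades for which no scheduled on-treatment value exists at C2. The renal part of that argument is weak, because protocol Table 3 lists blood urea nitrogen but not creatinine (SAP Section 12.7 does list it).

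Finally, SAP Section 5.1 reports the Stage 1 look in the past tense. A schedule change cannot alter that count. Nor do the documents show that the Stage 1 result was wrong.

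**Conclusion.** The concern holds for subjects who continue treatment. The plan counts Cycle 1 Grade 3/4 events, laboratory events included, but schedules no chemistry that could reveal one after Day 1 and date it to that cycle. The direction of bias, towards meeting the safety criterion, follows from the schedule alone.

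The size does not. It depends on the true Cycle 1 event rate and on how many subjects have an undetected chemistry abnormality as their only qualifying event, and the documents give neither. The assumed cases above run from a loss of about 2 percentage points in the chance of exceeding the limit to one of about 29. The range illustrates sensitivity and is not an estimate.

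**What to change.** 1. **Reconcile Section 6.1 with the Stage 1 criterion.** One data-collection option is to run the chemistry panel at the C2 Day 1 pre-dose blood draw, where hematology, serum ABA and cytokine samples are already scheduled. Sections 2.1 and 9.1.1 and SAP Section 4 should then say how those results feed the Cycle 1 count.
2. **Disclose the limitation.** Because the Stage 1 look has been done, state in the SAP and the study report that its Grade 3/4 count, and Cycle 1 Grade 3/4 chemistry rates generally, rested on no scheduled on-treatment chemistry for continuing subjects. Reporting how many Stage 1 subjects had any unscheduled post-dose chemistry in Cycle 1 would show how far this matters.
3. **Reconcile Table 1 with the chemistry schedule.** The sponsor should settle how the laboratory-graded pembrolizumab actions fit the times at which chemistry is available. No dosing or monitoring rule is proposed here.

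**Cost.** One extra chemistry panel per subject, with no new visit, plus a short text change. The existing rule already looks into Cycle 2 for recurrent infusion reactions and waits for Week 6 scans, so a C2 Day 1 result should not delay the decision. The downside is that, in any cohort still to be judged by the criterion, fuller detection may make it fail more often.
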